#### Human Subjects Protection

#### **Subject Recruitment Methods**

Several strategies will be implemented to assist with recruitment. Participants may be identified by screening provider schedules. They will be recruited by mailed recruitment letter, myWakeHealth message, telephone, and/or in person when presenting for their surgical consent or pre-operative assessment visit (as allowed by institutional and government policies).

Informational flyers describing the study will be disseminated to the orthopedic clinics at Davie Medical Center. Recruitment will also be done through the orthopedic clinic at the time of a patient's preoperative assessment visit in one of three ways: 1) patients will be given an informational flyer and instructed to call study phone line if interested in participating, 2) they may ask to receive a call from the study team, or 3) they may meet directly with a study team member the day of their pre-operative assessment visit if a study team member is available.

Study personnel will review eligibility questionnaire with participant (confirm age, date of preassessment appointment, date of surgery, type of surgery, presence of pacemaker or other electrical device, hearing aid use, skin disorder or allergies, current medications). If eligible based on phone or in person screen, study personnel will do second stage eligibility screen via WakeOne chart review to calculate current morphine equivalent, medical history for delirium, ASA status, and cognitive impairment or delirium. If eligible, participant will be consented by study personnel at their preassessment anesthesia visit or on the day of surgery. The study personnel will maintain a record of eligible study participants. This list will include name, MRN, surgery type, pre-assessment appointment, and surgery date will be kept in a secure file on a secure computer. The file of eligible participants will be destroyed at the end of recruitment.

#### **Informed Consent**

Signed informed consent will be obtained from each subject. The study personnel will obtain informed consent at the time of the pre-operative assessment or on the day of surgery. The AA nurse will be contacted to come and speak with patient to answer any questions prior to signing consent. During COVID-19, we plan to obtain consent remotely in cases where the study team is not able to have face to face contact with the participant. In order to obtain legally effective consent, the investigator or member of the study team will provide two copies of the approved consent form for documentation. After received, the study team member will speak with the participant, presenting the elements of consent, the content of the study, and answer any questions. At the end of the discussion, the study team. The study team will clarify that the second consent form should be kept by the participant for documentation. Upon receipt of the signed form, the study team member will sign and date with the current date, and add a note detailing the date discrepancy. No study procedures will begin until the IRB approved method of obtaining consent is completed. Participants will be reminded that if the signed consent form is not received prior to the surgery and if there is not a study team member available to consent prior to the surgery, they will not be able to participate in the study.

## **Confidentiality and Privacy**

Confidentiality will be protected by collecting only information needed to assess study outcomes, minimizing to the fullest extent possible the collection of any information that could directly identify subjects, and maintaining all study information in a secure manner. To help ensure subject privacy and confidentiality, only a unique study identifier will appear on the stored data collection forms. Any collected patient identifying information corresponding to the unique study identifier will be maintained on a linkage file, store separately from the data. The linkage file will be kept secure, with access limited to designated study personnel. Following data collection, subject identifying information will be destroyed three years after closure of the study, and files will be erased. Each study participant will be assigned a unique identifier that will be linked to their name. The participant study questionnaire will contain the patient's name and after collection of the study questionnaire from the patient, the study coordinator will replace the name on the study questionnaire with the participant's unique identifier and data will be transferred to the study data base with data validation producing an anonymous analytical data set. Data access will be limited to study staff. Data and records will be kept locked and secured with any computer data password protected. No reference to any individual participant will appear in reports, presentations, or publications that may arise from the study.

#### Data and Safety Monitoring

The principal and co- investigator will be responsible for the overall monitoring of the data and safety of study participants. They will be assisted by other members of the study staff. Although no serious safety events have been reported in the literature related to auricular acupressure, participants will be asked to report any events to study personnel. Participants will be instructed to monitor and report any concerns related to acupressure pads to the AA nurse on-call and these will be escalated to the PI and then to the Co-investigator for evaluation, if needed. The co-investigator or a licensed acupuncture provider at the Center for Integrative Medicine will serve as consulting physician/acupuncturist for any adverse event that is determined to be potentially related to the study, including physical examination and treatment if necessary.

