- Participants may stimulate both ear sites at the same time beginning with site 1 and ending with site 5. Studies have placed acupressure pads for 3-8 days depending on study outcomes (He et al., 2013; Yeh et al., 2014), the pads will be placed for a total of 5 days based on manufacturer's recommendation and the BAA protocol (See example of Earseeds instruction brochure). On the day of surgery, the participant will be informed to apply pressure one to 2 more times that day, depending upon the time the acupressure pads were placed. Participants will be informed that if any acupressure pads fall off while home, they are not to be replaced, but to record on the study questionnaire (see participant questionnaire). Staff nurses will remind participants to complete their questionnaires and to call the AA nurses with any questions related to the acupressure pads or the study.
- At time of discharge, the study personnel will ensure that the participant has participant questionnaire and the addressed and stamped envelope. Instructions for activation of the acupressure pads and questionnaire completion will be reviewed. Participants will be informed that they will either receive a phone call or text reminder twice daily to complete the questionnaire and to activate their pads 3 times per day. Participant is to continue to apply pressure to remaining pads until the end of the study.
- On post-operative day 4, the study personnel will call the patient and instruct them to remove the acupressure pads by gently pulling on the edges of the pad and lifting off with their fingers or using tweezers to loosen the pad if needed. Participants will be reminded to mail questionnaire in the provided postage paid envelope, if they have not done so already
- **Control Group:** The AA nurse will give participants in the control group the study questionnaire once they arrive to the floor and remind participant and family to complete the questionnaire as indicated. At time of discharge, study personnel will ensure that participant has study questionnaire and the addressed and postage paid envelope. Participants will be informed that they will either receive twice daily phone calls or text messages to complete the questionnaire. On postoperative day 4, study personnel will call and remind participate to mail questionnaire in the provided postage-paid envelope.

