## **Outcome Measure(s)**

- 1) Pain: Both inpatient and outpatient pain scores will be measured using the VAS as documented on the participant study questionnaire.
  - a. am pain score on rising aggregated over 4 days (post-op day 1 –post-op day 4)
  - b. pm (worse pain throughout the day) pain score aggregated over 5 days (post-op day 0 post-op day 4)
  - c. trajectory of am and pm pain scores
- 2) Inpatient opioid pain medication will be collected via the MAR in WakeOne. Outpatient usage will be self-reported in study questionnaire. Inpatient and outpatient total opioid use will be converted to total Morphine equivalent.
  - a. Total morphine equivalent aggregated over day 0-4
  - b. Trajectory of morphine equivalent from day 0 4
- 3) Overall participant satisfaction will be measured on post-op day 4 via participant questionnaire.
- 4) Nurse time will be measured in minutes from time AA nurse enters room to place acupressure pads to when AA nurse exits room. Qualitative questions will be used to assess overall feasibility of nurse initiated auricular acupressure.

| Outcome               | Measure         | Baseline | Post-op Day 1-2 | Post-op days
1-4 |
|-----------------------|-----------------|----------|-----------------|---------------------|
| Pain                  | Visual Analogue | X        |                 | Х                   |
|                       |                 |          |                 |                     |
| Medication            | WakeOne MAR     |          | Х               | Χ                   |
| Inpatient             | Participant     |          |                 |                     |
| -                     | Questionnaire   |          |                 |                     |
| Medication Use | Participant     |          |                 | Х                   |
| Outpatient            | Questionnaire   |          |                 |                     |
| Pellet Retention      | Participant     |          | X               | X                   |
| Days                  | Questionnaire   |          |                 |                     |
| Pain                  | Participant     |          |                 | Х                   |
| Management            | Questionnaire   |          |                 |                     |
| satisfaction          |                 |          |                 |                     |

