| Nurse Time            | Questionnaire   |          | X               |                     |
| Nurse Feasibility     | Questionnaire   |          | Х               |                     |

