## **Reporting of Unanticipated Problems, Adverse Events or Deviations**

Any unanticipated problems, serious and unexpected adverse events, deviations or protocol changes will be promptly reported by the principal investigator or designated member of the research team to the IRB and sponsor or appropriate government agency if appropriate.

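### The protocol defines no local ear tolerability outcome or harms summary, and the reporting it describes is likely to under-count local reactions to the pads

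*Combined protocol and SAP*

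**What the plan says.** **Capture of events.** Data and Safety Monitoring gives two routes. In general, "participants will be asked to report any events to study personnel". For the pads in particular, "Participants will be instructed to monitor and report any concerns related to acupressure pads to the AA nurse on-call", with escalation to the investigators and examination if needed. Neither route has a schedule, a form or a list of symptoms.

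**Onward reporting.** The section on unanticipated problems says that "serious and unexpected adverse events, deviations or protocol changes will be promptly reported". Mild skin reactions of an expected kind are not named.

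**Exposure.** Interventions and Interactions describes ten adhesive seed pads, five per ear, each pressed for 30 seconds three times a day, and says "the pads will be placed for a total of 5 days". The ear is inspected before placement, and the pads are withheld if it is irritated or broken. No matching check at removal is described.

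**Contacts after discharge.** "Participants will be informed that they will either receive a phone call or text reminder twice daily to complete the questionnaire"; these reminders also cover pad activation. Then, "On post-operative day 4, the study personnel will call the patient and instruct them to remove the acupressure pads", with a reminder to post the questionnaire. No question about the ears is described for any of these contacts.

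**Outcomes and analysis.** The table under Outcome Measure(s) has one pad item, "Pellet Retention". Its other rows are pain, inpatient and outpatient medication, satisfaction, nurse time and "Nurse Feasibility". The Analytical Plan names pain and morphine equivalents for modelling and plans no harms summary.

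**The concern.** The exclusions for adhesive allergy, latex allergy, ear skin disease and cuts, together with the inspection before placement, show that local skin effects are recognised as relevant. The study is a feasibility pilot, and acceptability of the treatment is objective 1c. A sore or broken ear bears directly on that objective, yet nothing in the protocol body turns it into a measured result.

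When capture depends on the participant deciding to report, mild and moderate reactions are the ones most easily left out. A report of no local events could then reflect how they were collected as much as how often they occurred, and that impression could carry over to a larger trial.

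The retention item does not fill the gap. As described, it counts pads that stay on. The protocol body does not say whether a pad taken off for discomfort is distinguished from one that fell off, and the two would call for different responses in a later trial.

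**Working it through.** The documents give no expected rate of local reactions and no capture rate, so there is no planned figure to reproduce. The steps below show how much a zero count would mean under stated assumptions.

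**Inputs**
- Treated participants: 30 recruited per arm (Sample Size).
- Lower end of the evaluable number: 24 per arm (same section), used here as a low case for how many might be assessed.
- Share of reactions reported, s: not in the documents. Values of 100%, 50% and 25% are assumed.
- True rate of local reactions, p: not in the documents. 10% is assumed where a rate is needed.

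**Step 1. Upper bound from zero events with complete capture.** The one-sided 95% bound is 1 − 0.05^(1/n).
- n = 30: 1 − 0.05^(1/30) = 9.5%.
- n = 24: 1 − 0.05^(1/24) = 11.7%.

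The upper limit of the two-sided 95% exact interval, 1 − 0.025^(1/n), is 11.6% for n = 30 and 14.2% for n = 24.

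**Step 2. The same bound with incomplete capture.** If each affected participant reports with probability s, a zero count bounds p × s, so the bound on p is the Step 1 value divided by s. For n = 30:

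| Assumed s | Upper bound on true rate |
|---|---|
| 100% | 9.5% |
| 50% | 0.095 / 0.50 = 19% |
| 25% | 0.095 / 0.25 = 38% |

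**Step 3. Chance of recording at least one reaction.** This is 1 − (1 − p × s)^30. At p = 10%, 3 reactions are expected among 30.

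| Assumed s | Expected number recorded | Chance of at least one |
|---|---|---|
| 100% | 3.0 | 96% |
| 50% | 1.5 | 79% |
| 25% | 0.75 | 53% |

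**Step 4. Where a question could be asked.** The day-4 call is planned for treated participants, so a contact already exists. However, its purpose is to tell participants to remove the pads, so the pads are normally still on when it begins. A checklist at the start of the call would miss anything seen only at removal. The list has to follow removal.

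**The case against.** The strongest objection is that the participant questionnaire, which is the trial's main data instrument, is listed as Appendix 1 but its items were not available. It may ask about the skin or about why a pad was lost. That limits what can be said. A reader might infer that nobody asks about the ears, or that events are captured only when volunteered. The documents do not support either statement, because the questionnaire may ask and because the monitoring section also says that participants will be asked to report events, without saying when or how. A reader might likewise infer that a pad removed for soreness is logged as a lost pad. The text covers recording of missing and fallen pads and is silent on deliberate removal, so that would be a guess about a form that was not available.

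Three further objections have weight. The 19% and 38% bounds rest wholly on assumed reporting shares and a hypothetical zero count. Safety is not a stated objective, while satisfaction and retention overlap partly with tolerability. The background cites 26 trials with no serious adverse events and no withdrawals due to adverse events, and the protocol has an escalation path.

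These points lower the priority but do not remove the gap. Absence of serious events and withdrawals says little about mild or moderate ear reactions. Whatever Appendix 1 contains, no listed outcome or analysis uses it.

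**Conclusion.** The point holds in a limited form. The protocol body prespecifies no local tolerability outcome and no harms summary, and no contact it describes asks systematically about ear symptoms. Under-counting of local reactions is likely. It is not certain, since the documents give no capture rate from which to establish its extent.

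The firm figure is the best case: zero events with every treated participant assessed would leave true rates up to 9.5% (n = 30) or 11.7% (n = 24) compatible with the data, one-sided 95%. The doubling to about 19% holds only if half of reactions are reported. It shows how the bound scales and does not estimate this trial's shortfall.

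No pain or opioid comparison is affected. This is an inexpensive improvement to the safety and acceptability information that the pilot can pass on.

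**What to change.** 1. Add a row for local ear tolerability to the outcome list and table.
2. Ask treated participants a fixed yes/no list, with worst severity for each positive: ear pain, itch, redness, blister or broken skin, and any pad removed early because of discomfort, recorded separately from pads that fell off.
3. Ask it after removal. Use the existing day-4 call if the participant takes the pads off while on the line, or put the same list on the mailed questionnaire as a post-removal line.
4. In the Analytical Plan, summarise as count and percentage with exact confidence interval among treated participants, and state how many were assessed.
5. Send positive answers through the escalation path already set out under Data and Safety Monitoring.

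If Appendix 1 already has a suitable item, it is enough to name it as the outcome and summarise it.

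The cost is a few extra minutes per treated participant and a short data form. More minor events will be recorded. The change concerns measurement only and leaves the treatment as it is.

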## **Reporting of Unanticipated Problems, Adverse Events or Deviations**

Any unanticipated problems, serious and unexpected adverse events, deviations or protocol changes will be promptly reported by the principal investigator or designated member of the research team to the IRB and sponsor or appropriate government agency if appropriate.

## Appendix

- 1. Participant Study Questionnaire
- 2. Nurse questionnaire
- 3. Consent form
- 4. Acupressure Sites
- 5. Davie Medical Center Total Joint Program Inclusion Criteria
